8.0 Sharing of Results with Subjects

- 8.1 Results will not be shared with the subjects of this study.

9.0 Study Timelines

- 9.1 Each participant will be involved in the study for approximately 3-4 months, including eligibility screening, baseline assessment, 4-6 weeks of intervention with daily EMA/EMI, post-intervention assessments, and a 3-month follow-up. We anticipate enrolling participants over a 2–3-month period. Primary analyses and study completion will be completed 6 months post data collection.

10.0 Inclusion and Exclusion Criteria

- 10.1 Screening survey: Individuals interested in the study will access a Qualtrics survey via recruitment links. The survey will be developed based on the study's inclusion and exclusion criteria (except for imminent risk of suicide and current Major Depressive Episode, which will be assessed during the Zoom screening interview). Scores on screening measures within the survey will be calculated in real time using Qualtrics' scoring feature—if a potential participant's score meets the study's inclusion threshold (see section 10.2), the survey flow will set an embedded variable ("eligible") to true; otherwise, it will be set to false. Statement addressing the legal concerns of underage consumption of alcohol and illegal substance use has been added to the screener.

Individuals who meet the eligibility criteria will be redirected to a separate Qualtrics form where they can review the Informed Consent Form (ICF) and complete a contact form, which will collect their full name and email address. These individuals will also be asked if they would like to be notified for future research. Please refer to the document named "Compiled measures_GEM.docx" for the screening survey, contact form, and future contact form. A trained research staff will then follow up with the eligible participants to schedule a Zoom-based screening interview.

Zoom screening interview: The interview will take 15-30 minutes to complete and will serve the following purposes: (a) confirm participant eligibility and identity by participant showing any form of ID including photo, name, and age; (b) review informed consent form; (c) review study procedures and answer any questions the participant may have; (d), screen for current Major Depressive Episode and imminent risk of suicide; and (e) inform the participant (if eligible and interested to enroll) of the next steps, which includes the next Zoom call meeting for baseline assessment and onboarding (refer to section 6.2). At the beginning of the screening call, RA will remind participants that if they disclose information indicating imminent risk of serious harm to themselves or others, this information must be reported to relevant law enforcement or other authorities. The RA conducting this interview will use a Qualtrics survey with the questions/measures that need to be administered (e.g., the MINI-Major

Depressive Episode module or the suicide screener), which will serve as their guide during the interview. The qualtrics survey will be accessed only by the RA (i.e., the survey won't be sent directly to the participant) and filled out by the RA as the interview progresses. The Qualtrics data will only be linked to the participant ID number (deidentified only) and will be kept in a secure location with other de-identified data. Please refer to "ICF Checklist_GEM.docx" for a full list of screening questions that will be asked, including screening for current Major Depressive Episode and suicidal ideation. To mitigate confidentiality risks and risk of third-party participants, participants will be instructed to complete the procedure in a private location. Participants will be reminded to pause the assessment if another person enters the space. Please refer to the document named "Compiled measures_GEM.docx" for the general structure of the interview and "ICF Checklist_GEM.docx" for more detailed interview guide to be used by the RA conducting the interview.

For participants who report suicidality in the MINI-Standard: Major Depressive Episode module or during the suicide screener, the suicide safety assessment and plan will be followed accordingly (refer to document named "Suicide Safety Plan_GEM.docx"). Because all eligible participants at this point will have only mild to moderately severe symptoms of depression (individuals with severe symptoms are screened ineligible at the Qualtrics screener survey), there is low likelihood that a participant will be at imminent risk of suicide; however, the suicide safety assessment and plan has been developed out of an abundance of caution.

The Suicide Safety Assessment and Plan will be conducted by [name], a licensed psychologist and the principal investigator of the study, or by a study team member who has been formally trained by [name] and operates under her direct supervision and oversight, consistent with existing clinical trial protocols for NIH-funded studies in the lab. All study personnel will receive training from [name] on identifying and responding to suicide risk. In addition, [name] will be on-call and will be notified immediately of any safety concerns.

10.2 Inclusion criteria:

- (1) Age 18-24
- (2) Reside in the US
- (3) Experiences of psychosocial forms of early life adversity, defined as saying yes to at least one of these following questions:
 - Did you ever miss school due to fear of being bullied?
 - Were you ever injured or threatened with a weapon or otherwise assaulted by a peer at school?
 - Were you ever physically attacked, hit, hurt, or injured by a parent, primary caregiver, or guardian?
 - Were you ever touched sexually against your wishes or forced to touch someone else sexually?
 - Were you ever forced to engage in sexual intercourse?
 - Were you ever forced to have sex or were you ever sexually abused (e.g., being touched or fondled by an adult?)

- (4) Experience more than minimal symptoms of anxiety (GAD-7 score of 5 or higher) and/or mild to moderately severe depression symptoms (PHQ-9 score between 5–19)
- (5) Not currently in mental health treatment
- (6) Being willing to answer 3–4 short surveys daily, each 2–5 mins
- (7) Being willing to engage in recommended daily mindfulness practices for 4–6 weeks
- (8) Have not been extensively exposed to mindfulness, defined as meditation retreat experience, consistent mindfulness practice (> once/week) within the past 6 months, or prior participation in a mindfulness course/program

Exclusion criteria:

- (1) At imminent risk of suicide
- (2) Have a history of psychotic disorder (e.g., schizophrenia) or psychotic episode
- (3) Have a current diagnosis of Major Depressive Disorder
- (4) Meet the criteria for Major Depressive Episode based on the MINI-Major Depressive Episode module at screening
- (5) Score 20 or higher on Alcohol Use Disorders Identification Test (AUDIT) at screening
- (6) Score 25 or higher on Drug Use Disorders Identification Test (DUDIT) at screening
- (7) Have ever been diagnosed with bipolar disorder

10.3 We will not include any of the listed special populations in this research.

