3.0 Background

- 3.1 mHEAL research team has extensive experience in developing and evaluating mindfulness-based, transdiagnostic interventions for young adults. Examples include Mindfulness-based Queer-Resilience (with over 200 pages of materials, 30+ created videos, and 50+ recorded audios in our lab library) for young adults with depression/anxiety and affected by trauma, stigma, and childhood adversity as well as Mindfulness for Pandemic Resilience, a mobile app for youth in China with psychiatric symptoms and affected by strict pandemic lockdowns. Both programs have been evaluated by RCTs and shown acceptability, feasibility, and preliminary efficacy. Findings showed that the intervention was efficacious especially for participants with experiences of early life adversities. However, there has not been a mindfulness intervention tailored specifically towards young adults who have lived experiences of early life adversities, representing an important opportunity for action. Further, studies that examine mechanisms underlying specific mindfulness practices and their effectiveness at addressing specific stressors are lacking.
- 3.2 N/A
- 3.3 Facing early life adversity is common among the United States population, with one epidemiological study finding that 53.4% of surveyed participants had experienced at least one adverse childhood event (Green et al., 2010). Early life adversity has been associated with poorer mental health, which can also contribute to a greater likelihood of engaging in risky health behaviors (Duffy et al., 2018). Additionally, early life adversity has been associated with alterations in neural functioning and compromised emotional regulation skills (Krugers et al., 2017). Mindfulness interventions have been found to reduce symptoms of anxiety and depression (Hofmann & Gómez, 2018) and improve emotional regulation abilities (Goldin &

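### Inclusion criterion (3) sets no age at exposure, so as printed it accepts adult-only events as early life adversity

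*Protocol*

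**What the plan says.** Protocol section 10.2, criterion (3), sets the exposure that defines the study population: "Experiences of psychosocial forms of early life adversity, defined as saying yes to at least one of these following questions". Six questions follow, two about school, one about a caregiver and three about sexual violence, among them "Were you ever touched sexually against your wishes or forced to touch someone else sexually". Criterion (1) limits age at enrolment to 18–24. Nothing limits age at the event.

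The background (section 3.3) introduces the exposure through a survey in which "53.4% of surveyed participants had experienced at least one adverse childhood event". The title and the objectives in section 2.1 name young adults with early life adversities as the population.

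Under section 10.1 the online screener is built from these criteria and sets eligibility automatically. A Zoom interview then confirms it. Section 6.2 lists baseline (T1) scales for early life adversity and childhood trauma, and a separate one for stress and adversity experiences. The SAP names severity of early adversity as one example of a baseline covariate in the mixed-effects model, under its heading on pre-post changes.

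**The concern.** The rule that decides who enters is wider than the population the study says it is about. For people aged 18 to 24, a lifetime question covers both childhood and adult events, and criterion (3) does not separate them. Someone assaulted for the first time as an adult, with no earlier adversity, satisfies it.

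What is at stake is whom the results describe. The SAP's benchmarks for recruitment, retention, satisfaction and adherence, and the pre-post changes in depression and anxiety, are meant to inform a programme tailored to early adversity. If some participants have none, those figures describe a mixed group, and the plan has no step that would show the mixture.

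**Working it through.** No arithmetic settles this point, and the plan gives no figure to reproduce. The check is to read the criterion item by item, then look for any other place that supplies the missing limit.

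**Step 1: the six items in printed order.**

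| Item | Age limit | Setting or perpetrator limit |
|---|---|---|
| 1. "Did you ever miss school due to fear of being bullied" | none | school |
| 2. "Were you ever injured or threatened with a weapon or otherwise assaulted by a peer at school" | none | peer, at school |
| 3. "Were you ever physically attacked, hit, hurt, or injured by a parent, primary caregiver, or guardian" | none | parent or caregiver |
| 4. "Were you ever touched sexually against your wishes or forced to touch someone else sexually" | none | none |
| 5. "Were you ever forced to engage in sexual intercourse" | none | none |
| 6. "Were you ever forced to have sex or were you ever sexually abused (e.g., being touched or fondled by an adult" | none | none in the first half; the example in the second half suggests a child respondent |

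Items 1 to 3 mostly point to youth by context, although school and parents can still be present at 18 or later. The gap is clearest in items 4 and 5 and the first half of item 6.

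**Step 2: apply the rule.** Take a 23-year-old whose only event, unwanted sexual touching, occurred at age 20. Items 1 to 3 are no and item 4 is yes. One yes is enough, so criterion (3) is met. The other criteria must still be satisfied.

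**Step 3: how long the adult window can be.** It runs from the 18th birthday to enrolment. For someone newly 18 it is close to zero. For someone about to turn 25 it is at most 25 − 18 = 7 years.

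**Step 4: look for a limit elsewhere.**
- Neither document gives an age for early life.
- Section 10.1 has the Zoom interview confirm eligibility but describes no check of age at exposure.
- The T1 adversity and trauma scales in section 6.2 are baseline measures and are not stated as entry conditions.
- The SAP uses early adversity only as a covariate and plans no description of participants without it.
- Criterion (8) does set a period, the past 6 months, for prior mindfulness practice. The protocol states time windows where it wants them.

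**Step 5: size.** The documents give no distribution of age at exposure, so the expected number affected cannot be calculated. The only available scale is that each such participant is 1/44 = 2.3% of planned enrolment, or 1/35 = 2.9% of the target number of completers in section 12.2.

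**The case against.** The strongest objection is that the screener itself has not been seen. Section 10.1 places it in a separate measures file and the interview questions in a separate checklist. Either could carry a lead-in restricting the items to childhood. This stands: the documents support a statement about the printed criterion, not about what respondents read. A reader might infer that people with adult-only events will be enrolled; that goes further than the text allows.

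Second, several items lean towards youth, and section 13.2 names foster care and youth residential programmes among the sources, which favours childhood exposure. This also stands and narrows the gap. It does not close it: the same section names networks for survivors of abuse and violence, and section 13.1 includes campus groups, neither limited to childhood events.

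Third, section 7.1 does not keep the screener survey answers, and a reader might infer that the problem could never be traced. That does not follow. The T1 adversity and trauma data are collected under section 6.2 and kept indefinitely under section 7.1, so such participants can probably be identified afterwards. Identification does not restore the intended sample, however, and the SAP does not plan it.

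Two further inferences are tempting and unsupported. One is that recent adult trauma would fade on its own and inflate the pre-post change. Neither document says so, and uncontrolled change over time affects every participant in a single-arm trial, so an age limit would not remove it. The other is that the severity covariate would be near zero for these people. The SAP does not name the measure and its wording was not supplied.

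**Conclusion.** The point holds for the protocol text. Criterion (3) admits people outside the population named in the title and objectives, most plainly through items 4 and 5 and the first half of item 6, and no described step removes them. This is more than a missing detail, because this criterion defines the study population.

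The size is unknown. Any percentage of the 44 would be a guess, and nothing in the documents shows that a benchmark decision would change. The pilot is not invalidated. The conclusion assumes that the screener repeats the items as printed. If it already has an age-bounded lead-in, what remains is a mismatch between section 10.2 and the screener. The later count assumes that at least one T1 scale is limited to childhood, as the childhood trauma label suggests but the documents do not confirm.

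**What to change.** 1. Put one age-bounded stem before all six items, in the same words in criterion (3) and in the screener. *Before you turned 18* is one option. The documents set no cut-off, so the age bound of the T1 early-life-adversity or childhood-trauma scale, if it has one, would serve equally and keep screener and scale aligned.
2. If the screener already has such a stem, confirm this and amend section 10.2 to match.
3. Add to the SAP a count of enrolled participants with no childhood event on the T1 early-life-adversity and childhood-trauma scales. Repeat the retention, satisfaction, EMA and audio-module benchmarks and the pre-post changes without them. The recruitment benchmark cannot be repeated this way, because its denominator includes people who never reach T1.

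The cost is one phrase in the protocol, one stem in the screener and a short addition to the SAP using data already collected. The downside is that somewhat fewer people will screen positive; the documents do not allow that number to be estimated.

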Further, as described in “Compiled Measures_GEM.docx”, for any participant saying Yes to question A3.g in the MINI-Major Depressive Episode module, the suicide safety and assessment plan will be automatically triggered through Qualtrics by redirecting the RA to a message telling them to stop assessment and administer the safety and assessment plan (refer to document named “Suicide Safety Plan_GEM.docx”). Because all eligible participants at this point will have only mild to moderately severe symptoms of depression (individuals with severe symptoms are screened ineligible at the Qualtrics screener survey), there is low likelihood that a participant will be at imminent risk of suicide; however, the suicide safety assessment and plan has been developed out of an abundance of caution. The Suicide Safety Assessment and Plan will be conducted by [name], a licensed psychologist and the principal investigator of the study, or by a study team member who has been formally trained by [name] and operates under her direct supervision and oversight, consistent with existing clinical trial protocols for NIH-funded studies in the lab. All study personnel will receive training from [name] on identifying and responding to suicide risk. In addition, [name] will be on-call and will be notified immediately of any safety concerns. Participants who have active suicide ideation according to the suicide safety assessment will be excluded from the study, and study staff will take actions according to the suicide assessment and safety plan (please refer to “Suicide Safety Plan_GEM.docx”).

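### Inclusion criterion 4 can be met on GAD-7 alone at any PHQ-9 score, while three safety statements say that severe depression symptoms are screened out at the online survey

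*Protocol*

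**What the plan says.** **The criterion.** Protocol Section 10.2, inclusion criterion 4, has two branches, joined in these words: "GAD-7 score of 5 or higher) and/or mild to moderately severe depression symptoms". The first is "Experience more than minimal symptoms of anxiety (GAD-7 score of 5 or higher) and/or"; the second follows directly: "and/or mild to moderately severe depression symptoms (PHQ-9 score between 5–19". Section 13.3 likewise describes potential participants as identified through self-reported depression or anxiety symptoms.

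**How it is applied.** Section 10.1 says the online survey is built on the inclusion and exclusion criteria, "except for imminent risk of suicide and current Major Depressive Episode, which will be assessed during the Zoom screening interview". Scores are computed in real time, and if the Section 10.2 threshold is met "the survey flow will set an embedded variable" that marks the person as eligible.

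**The exclusions.** The seven exclusion criteria cover imminent suicide risk, psychotic history, a current diagnosis of Major Depressive Disorder, a Major Depressive Episode on the MINI at screening, AUDIT, DUDIT and bipolar disorder. None refers to PHQ-9.

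**The safety statements.** Section 6.2 (assessments at T1, T2 and T3), Section 10.1 (Zoom screening interview) and Section 18.1 (safety monitoring) carry the same reasoning. Everyone eligible is said to lie in the mild to moderately severe depression range, since "individuals with severe symptoms are screened ineligible at the Qualtrics screener survey". From this the protocol concludes that "there is low likelihood that a participant will be at imminent risk of suicide".

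**The concern.** The safety statements credit the online survey with a property that the written eligibility rule does not give it. The upper PHQ-9 limit is part of one of two alternative routes into the study, so it does not bind anyone who enters by the other route.

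The sentence matters because it is offered as the reason for expecting low suicide risk, and it appears in the safety-monitoring section as well as in the procedures. Anyone relying on the protocol to judge risk is given a premise that Section 10.2 does not deliver. The practical difficulty is that whoever programs or checks the survey has two incompatible descriptions to work from: Section 10.2, with no general ceiling, and the three safety statements, which presuppose one. PHQ-9 is also the SAP's example measure for depression, one of its primary clinical targets, so the range of scores allowed at entry should be unambiguous.

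**Working it through.** The plan gives no figure to reproduce. The check is one of logic, with a count to show its extent.

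**Inputs**
- Anxiety branch: GAD-7 ≥ 5, with no PHQ-9 condition (Section 10.2, criterion 4).
- Depression branch: 5 ≤ PHQ-9 ≤ 19 (same criterion).
- PHQ-9 conditions among the exclusions: none (Section 10.2).
- Scale ranges: GAD-7 from 0 to 21 and PHQ-9 from 0 to 27. The documents do not give these, so they are an assumption. They affect the counts but not the logic.

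**Rule as written.** Criterion 4 is met if (GAD-7 ≥ 5) OR (5 ≤ PHQ-9 ≤ 19).
- PHQ-9 = 24, GAD-7 = 12: the first branch is true, so the criterion is met.
- PHQ-9 = 2, GAD-7 = 8: the first branch is true, so the criterion is met.

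**All score pairs.** There are 22 GAD-7 values and 28 PHQ-9 values, giving 22 × 28 = 616 pairs. GAD-7 is 5 or more for 17 values and 0 to 4 for 5 values.

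| PHQ-9 | Pairs | Meet criterion 4 | Fail |
|---|---|---|---|
| 0–4 | 5 × 22 = 110 | 5 × 17 = 85 | 25 |
| 5–19 | 15 × 22 = 330 | 330 | 0 |
| 20–27 | 8 × 22 = 176 | 8 × 17 = 136 | 8 × 5 = 40 |
| All | 616 | 551 | 65 |

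The safety statements require the entry of 136 to be 0. It is 0 if the limit of 19 applies to everyone (85 + 330 = 415 pairs then pass), and also if both branches are required together. The text says neither.

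**Order of screening.** Section 10.1 leaves only imminent suicide risk and current Major Depressive Episode to the Zoom interview. The MINI therefore follows the online survey and cannot be what makes people ineligible at that survey. In Section 10.1 the safety statement describes people who have just reached the Zoom interview, before any MINI result exists. The exclusion "Have a current diagnosis of Major Depressive Disorder" depends on a diagnosis, not on a score.

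**Lower end.** The 85 pairs with PHQ-9 of 0 to 4 also lie outside the range in which the safety statements place everyone eligible. This is a second mismatch, but it does not touch the argument about suicide risk.

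**The case against.** The best case for the plan is that the sentence is only explanatory and that the real protection lies elsewhere. Someone who satisfies criterion 4 must still be out of current mental health treatment and pass the exclusions for imminent suicide risk, a current Major Depressive Disorder diagnosis and a MINI-defined episode. A separate suicide screener is given at the Zoom interview. By T1 every participant has passed those steps, so for Section 6.2 the low-risk expectation has support that does not depend on a PHQ-9 ceiling. The MINI is repeated at T1, T2 and T3, and a positive answer to item A3.g triggers the safety plan whatever the PHQ-9 score.

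All of this stands, and it rules out some stronger conclusions that a reader might draw:
- *That people with PHQ-9 of 20 or more will be enrolled.* Meeting criterion 4 is not enrollment. The later steps may remove many of them, and the documents give no basis for a number.
- *That the survey is miscoded.* The survey is in a separate file that was not available. Section 10.1 ties the flag to Section 10.2, but the safety statements describe a survey that rejects severe symptoms. The code could follow either.
- *That participants are left unprotected.* No screening or monitoring step is conditional on the disputed premise.

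The objection does not make the statement true. The protocol attributes the screen-out to the online survey, not to the MINI, and nothing in it says that a PHQ-9 of 20 or more implies a positive MINI. If the survey does contain a general ceiling, it departs from Section 10.2 and the protocol still needs correcting.

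**Conclusion.** The contradiction is established on the text. Section 10.2 has no PHQ-9 ceiling for those who qualify on anxiety, whereas Sections 6.2, 10.1 and 18.1 assert that the online survey applies one and base a safety expectation on it. It is sharpest in Section 10.1, where no later screening result yet supports the claim.

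In terms of the rule, every PHQ-9 score of 20 or more satisfies criterion 4 once GAD-7 reaches 5: 136 of 176 score pairs, on the assumed scale ranges. This is not a proportion of participants, and the effect on enrollment is unknown. What is wrong is the agreement between the eligibility rule and its stated safety rationale; the safeguards themselves remain in force. It should still be corrected, because it concerns who may enter and the reason given for expecting low suicide risk, and because automatic scoring applies whatever condition is programmed, not what was meant.

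The conclusion rests on reading *and/or* as either branch sufficing, which is its ordinary sense and agrees with Section 13.3.

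**What to change.** Reconcile criterion 4 in Section 10.2 with the statements in Sections 6.2, 10.1 and 18.1, then confirm that the condition behind the survey's eligibility flag matches the reconciled text. Either of two routes would make the passages agree:

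1. State in Section 10.2 the limit that the safety statements presuppose, as a condition that applies whichever branch a person enters by. The description of those eligible also needs rewording, because PHQ-9 scores of 0 to 4 would still qualify through anxiety.
2. Keep criterion 4 as it is, remove the screen-out statement from all three sections, and rest the safety rationale on the MINI and the suicide screening.

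Which rule is intended is for the sponsor to decide. The cost is a short text change and a check of one survey condition. The first route would add some unknown number of screen failures; the documents do not allow an estimate.
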